Up to 43 patients will be enrolled with metastatic/recurrent ACC of any site of origin with evidence of disease progression who are not candidates for curative surgical or radiation therapy. An exploratory cohort of 20 patients with non-ACC of major or minor salivary glands will be enrolled concurrently.

**The first 15 ACC patients will be assessed for safety, and ACC accrual will be terminated if ≥ 7 patients are withdrawn after <24 weeks of treatment for any reason other than withdrawal of consent. Otherwise, enrollment will continue for a total of 43 ACC patients. The exploratory cohort of 20 non-ACC MSGT's will follow an independent accrual process to ACC and will also be assessed for safety; if >2 of the first 10 non-ACC patients are withdrawn after <24 weeks of treatment, the non-ACC cohort will be closed to accrual.

[figure not shown]

NU Study Number: NU 16N03
BMS Study Number: CA 209-802

STUDY SUMMARY

Title	Phase II study of nivolumab and ipilimumab for treatment of metastatic/recurrent adenoid cystic carcinoma of all anatomic sites of origin and non-adenoid cystic carcinoma malignant tumors of the salivary gland
Version	October 6, 2022, Amendment 8
Study Design	Simon two-stage single arm multi-center phase II clinical trial
Study Center(s)	Northwestern University
Objectives	
Primary:
 
 (1) To assess median progression-free survival (PFS) as well as PFS at 6 and 12 months in patients with recurrent or metastatic adenoid cystic carcinoma treated with a combination of nivolumab and ipilimumab. 
Secondary:
 
 (1) To assess the efficacy of nivolumab and ipilimumab according to response rate (RR), disease control rate (DCR) or clinical benefit rate (CBR) at 6 and 12 months- defined as sum of CR, PR, and SD, overall survival (OS) and progression free survival (PFS) in the above population using RECIST criteria. (2) To assess the efficacy of nivolumab and ipilimumab according to ORR, DCR, PFS, and OS in the above population using immune-related RECIST (irRECIST) criteria. (3) To assess the safety and tolerability profile of nivolumab and ipilimumab therapy in the above population using CTCAE version 4.03 
Exploratory:
 
 (1) To assess the immune-related biomarkers and their association with treatment response (2) To assess activity of nivolumab and ipilimumab in non-ACC malignant salivary gland tumors (MSGTs) using OS, PFS, CBR, and ORR

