Statistical Methodology	
The main outcome is median Progression Free Survival (PFS) as well as PFS at 6 and 12 months. The optimal two-stage design to test the null hypothesis that $P \leq 0.450$ versus the alternative that $P \geq 0.650$ has an expected sample size of 24.70 and a probability of early termination of 0.654. If the drug is actually not effective, there is a 0.048 probability of concluding that it is (the target for this value was 0.050). If the drug is actually effective, there is a 0.196 probability of concluding that it is not (the target for this value was 0.200). After testing the drug on 15 ACC patients in the first stage, ACC accrual will be terminated if 7 or more patients are withdrawn from the study after <24 weeks of treatment for any reason other than withdrawal of consent (this includes PD, toxicity, intolerance etc.). If the trial goes on to the second stage, a total of 43 patients will be studied. If the total number responding (where response is defined as stable disease or better) is less than or equal to 24, the drug is rejected. An additional exploratory group of 20 patients with non-ACC MSGT will be added concurrently with ACC patients for a total samples size of 63 patients. An additional safety analysis will take place for non-ACC patients; if >2 of 10 non-ACC patients are withdrawn after <24 weeks of treatment, accrual of non-ACC patients will discontinue. Response rates and 95% confidence intervals will be calculated using exact binomial probability distributions for discrete outcomes. Progression-free survival and overall survival will be graphically depicted using Kaplan-Meier curves. Adverse events will be summarized descriptively using frequencies and percentages. Statistics will be given on type, severity, frequency and attribution of adverse events. Sample size considerations are described above.

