2.2 Secondary Objectives & Endpoints

2.2.1 To assess the efficacy of nivolumab and ipilimumab according to response rate (RR), disease control rate (DCR; CR, PR, and SD at 6 and 12 months), overall survival (OS) and progression free survival (PFS) using RECIST criteria in patients with recurrent or metastatic ACC. ⁴⁴

The time in months from start of treatment to progression or death will be measured for all patients who receive at least one dose of study drug. Patients will be followed up to 2 years after completion of treatment. Efficacy will be evaluated in all patients who receive at least one cycle of study treatment.

2.2.2 To assess the efficacy of nivolumab and ipilimumab according to ORR, DCR, PFS, and OS in patients with recurrent or metastatic ACC using irRECIST criteria.⁴⁵ Efficacy will be evaluated in all patients who receive at least one dose of study treatment and have had their disease re-evaluated.

2.2.3 To assess the safety and tolerability profile of nivolumab and ipilimumab therapy in patients with recurrent or metastatic ACC using CTCAE version 4.03. The number, frequency, and severity of adverse events will be collected from time of consent until 30 days after study treatment for all patients who receive at least one dose of study drug.

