10.0 STATISTICAL CONSIDERATIONS

10.1 Study Design/Study Endpoints

This is a single arm open label phase II clinical trial which will assess the anti-tumor efficacy of nivolumab in combination with ipilimumab in ACC. As these two monoclonal anti-bodies already have been studied and approved as monotherapy or combination in other histological tumor types we believe that a phase II study is appropriate for development of these drugs in metastatic/recurrent adenoid cystic carcinoma (ACC). The non-adenoid cystic carcinomas (non-ACC) of major or minor salivary glands are for exploratory purposes for signal finding and will not be included in our statistical plan.

10.1.1 Primary:

To assess the median progression-free survival (PFS) as well as PFS at 6 and 12 months [defined as the absence of death and of progression of disease] in patients with metastatic/recurrent and progressive ACC. The Response Evaluation Criteria in Solid Tumors (RECIST 1.1) criteria will be used for objective tumor response assessment

10.1.2 Secondary:

- (1) To assess the efficacy of nivolumab and ipilimumab according to response rate (RR), disease control rate (DCR; CR, PR, and SD at 24 weeks), overall survival (OS) and progression free survival (PFS) in the above population using RECIST criteria.
- (2) To assess the efficacy of nivolumab and ipilimumab according to ORR, DCR, PFS, and OS in the above population using irRECIST criteria.
- (3) To assess the safety and tolerability profile of nivolumab and ipilimumab therapy in the above population using CTCAE version 4.03
- (4) To assess the immune-related biomarkers and their association with treatment response
- (5) Assess activity of nivolumab and ipilimumab in non-ACC malignant salivary gland tumors (MSGTs)

10.1.3 Exploratory endpoints:

- To assess the predictive value of baseline immunosuppressive biomarker PD-L1 protein on tumor cells and the expression level and localization of

NU Study Number: NU 16N03
BMS Study Number: CA 209-802

other markers of inflammatory/immune signature. Correlations between cell free tumor DNA and tumor tissue genomic aberrations with anti-tumor efficacy of nivolumab/ipilimumab combination will be explored.

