10.2 Sample Size and Accrual

A Simon two stage optimum Phase II design will be used ⁴⁶. The main outcome is median Progression Free Survival (PFS) as well as PFS at 6 and 12 months. The optimal two-stage design to test the null hypothesis that $P \leq 0.450$ versus the alternative that $P \geq 0.650$ has an expected sample size of 24.70 and a probability of early termination of 0.654. If the drug is actually not effective, there is a 0.048 probability of concluding that it is (the target for this value was 0.050). If the drug is actually effective, there is a 0.196 probability of concluding that it is not (the target for this value was 0.200). After testing the drug on 15 patients in the first stage, ACC accrual will be terminated if 7 or more patients are withdrawn from the study after <24 weeks of treatment for any reason other than withdrawal of consent (this includes toxicity, PD, intolerance etc.) If the trial goes on to the second stage, a total of 43 patients will be studied. If the total number responding (defined as stable disease or better) is less than or equal to 24, the drug is rejected. An exploratory group of 20 patients with MSGTs will be included in the study, in addition to the 43 patients mentioned above. They can be enrolled in any order within the total accrual of 63 patients and will not participate in statistical analysis. A separate safety analysis will take place; if >2 of the first 10 non-ACC patients are withdrawn after <24 weeks of treatment, non-ACC accrual will discontinue.

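### The Simon figures in 10.2 belong to a stop at 7 or fewer successes in 15 on one endpoint; the plan stops at 7 or more withdrawals and then counts a different, untimed outcome

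*Combined protocol and SAP*

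**What the plan says.** Section 10.2 names a Simon optimal two-stage design testing P of 0.45 or less against 0.65 or more. It says the design "has an expected sample size of 24.70 and a probability of early termination of 0.654", with a 0.048 chance of a false positive and a 0.196 chance of a false negative. P is not defined. The sentence before these figures reads "The main outcome is median Progression Free Survival (PFS) as well as PFS at 6 and 12 months".

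- **Stage 1 rule, 10.2.** With 15 ACC patients, "ACC accrual will be terminated if 7 or more patients are withdrawn from the study after <24 weeks of treatment". Withdrawn consent is the one exception; PD, toxicity and intolerance all count.
- **Same rule elsewhere.** The count of 7 recurs in the Study Schema ("patients are withdrawn after <24 weeks of treatment for any reason other than withdrawal of consent"), the Study Summary and 4.5. Section 4.5 presents it as an interim safety analysis, speaks of discontinuation, and has no consent exception for ACC.
- **Final rule.** Section 10.2: "If the total number responding (defined as stable disease or better) is less than or equal to 24, the drug is rejected". The Study Summary agrees ("where response is defined as stable disease or better"). Neither gives a time point.
- **Timing of disease control.** Section 10.1.2 has "disease control rate (DCR; CR, PR, and SD at 24 weeks"; section 2.2.1 has "disease control rate (DCR; CR, PR, and SD at 6 and 12 months". The decision rule refers to neither.
- **Another accrual stop.** Sections 8.1.11 and 8.2.11 say enrollment stops after 12 participants if no tumor has shrunk. Section 10.2 does not mention this.
- **Denominator.** Sections 6.2 and 6.8 require a dose of nivolumab and a re-evaluation of disease. Section 10.3 analyses all patients evaluated and registered, whatever treatment they received.

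**The concern.** The error rates of a Simon design hold when the same yes/no outcome is counted at both looks with the stated cuts. Two things here depart from that.

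First, the cut. The number 7 is the design's bound on successes, but the plan applies it to withdrawals, which are failures. On the failure scale the matching bound is 8.

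Second, the outcome. Stage 1 counts leaving treatment; the final rule counts disease status. The plan lets them part in both directions. Under 4.4 a patient may stay on drug after RECIST progression, and so is retained at stage 1 but may fail at the end. Under 4.8 a patient who stops for toxicity without progression is still imaged, and a later response is counted, so a stage 1 failure can be a final success.

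This is the ACC cohort's formal go/no-go rule. A reader of 10.2 would believe that an active regimen has about an 80% chance of passing, while the written rule may give it materially less.

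**Working it through.** **Inputs, all from 10.2:** n1 = 15, n = 43 (so 28 in stage 2), final rejection at 24 or fewer, p0 = 0.45, p1 = 0.65.

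**Formulas.** Let X be the stage 1 successes, binomial(15, p), with a stop if X ≤ r1.
- Early termination: PET = P(X ≤ r1).
- Probability of a go: sum over x from r1+1 to 15 of P(X = x) × P(Bin(28, p) ≥ 25 − x). This is alpha at p0 and power at p1.
- Expected size: EN = 15 + 28 × (1 − PET), at p0.

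**Step 1: reproduce the plan, then apply the written cut.** Seven or more withdrawn of 15 means 8 or fewer not withdrawn. If withdrawal is taken as failure, r1 = 8.

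| Stop at stage 1 | PET at 0.45 | EN at 0.45 | Alpha | Power | PET at 0.65 |
|---|---|---|---|---|---|
| ≤6 successes | 0.452 | 30.34 | 0.054 | 0.847 | 0.042 |
| ≤7 successes (≥8 failures) | 0.6535 | 24.70 | 0.0481 | 0.8035 | 0.113 |
| ≤8 successes (≥7 failures, as written) | 0.818 | 20.09 | 0.0367 | 0.704 | 0.245 |

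The middle row matches all four quoted figures: EN = 15 + 28 × 0.3465 = 24.70, and beta = 1 − 0.8035 = 0.1965. A search over two-stage designs with alpha at most 0.05 and power at least 0.80 also returns 7/15 and 24/43 as the optimum. The written row has EN = 15 + 28 × 0.1818 = 20.09 and beta = 1 − 0.704 = 0.296.

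**Step 2: let withdrawal and outcome differ.** Take the final count as progression-free at 24 weeks. Let t be the share of progression-free patients off drug before 24 weeks, and k the share of progressed patients still on drug. The documents give neither, so both are assumptions, here held equal under both hypotheses.

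| k | Power at t = 0 / 5 / 10 / 20% | PET at 0.45, t = 0 / 10% |
|---|---|---|
| 0% | 0.704 / 0.624 / 0.534 / 0.346 | 0.818 / 0.898 |
| 20% | 0.808 / 0.761 / 0.697 / 0.531 | 0.516 / 0.654 |

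**Step 3: bound the false-go probability.** An early stop can only remove chances of a go. With a final count whose null rate is 0.45, the probability therefore cannot exceed P(Bin(43, 0.45) ≥ 25) = 0.0576.

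**Step 4: the untimed reading.** Suppose SD at any scan counts, P is a 24-week rate of 0.45, and the null rate of SD or better is 0.50 to 0.67. (The upper value is 0.45^(12/24) = 0.67, under exponential PFS.) These are assumptions. The false-go probability is 0.08 to 0.18 with k = 0 and t = 0, 0.03 to 0.05 with k = 0 and t = 20%, and 0.13 to 0.46 with k = 20% and t = 0.

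**Step 5: the 12-participant stop.** If shrinkage means objective response (assumption), the chance of none in 12 is 0.945^12 = 0.51 at the 5.5% historical rate in section 1.1, and 0.90^12 = 0.28 at an assumed 10%.

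**The case against.** The strongest reply is that the written rule can behave much as quoted. Section 4.4 ties treatment past confirmed progression to continuing clinical benefit, so more progressed patients may stay on drug when the drug works. With no non-progression stops, 12% of progressed patients on drug under the null and 20% under the alternative, the written rule gives PET 0.651, EN 24.77, alpha 0.045 and power 0.808. That is essentially the quoted set. This stands. A reader might infer that no scenario reproduces the quoted figures, but that needs equal rates under both hypotheses, which the documents do not state. What remains is that the figures are not guaranteed: they need particular values that the plan neither states nor justifies.

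A reader might also infer an inflated type I error. The documents do not support this in general. If withdrawal equals failure, the written cut lowers alpha to 0.037, and a 24-week final count caps it at 0.058. Larger values need the untimed reading together with assumed SD rates.

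Two further replies have weight. Section 4.5 calls the withdrawal stop a safety analysis, and a sponsor may well want one; its existence is not the fault. And the primary objective is estimation of PFS, displayed by Kaplan-Meier, which the wrong cut does not bias directly. Neither makes the quoted operating characteristics describe the written decision rule.

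The 12-participant stop may be carried over from another protocol, since 8.2.11 names anal cancer. It is still current text.

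**Conclusion.** The concern holds in this form. The quoted figures are arithmetically correct for a rule that the plan does not contain. On the simplest reading, with withdrawal equal to failure, the written rule raises beta from 0.196 to 0.296. It also raises the chance of stopping a regimen with P = 0.65 at stage 1 from 0.113 to 0.245. Early termination under the null becomes 0.818 instead of 0.654.

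Beyond that reading, the size depends on two rates that the documents do not give. Over the assumed values shown, power runs from 0.35 to 0.81. The likelier harm under a 24-week final count is lost power or a weaker early stop, with false-go at most 0.058.

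Correcting the cut alone would not make the quoted figures valid while the 12-participant stop in section 8 stands.

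**What to change.** 1. **Define P** in 10.2 and the Study Summary as one timed binary endpoint matching the primary: alive and progression-free by RECIST 1.1 at the 24-week assessment. Use it for the final rule of 24 or fewer in 43.
2. **Reconcile the stage 1 rule** across the Study Schema, Study Summary, 4.5 and 10.2, including the consent exception. Either state a futility look on the same endpoint at 7 or fewer successes in 15, to which the quoted figures belong, with any withdrawal-based safety stop stated separately; or keep the stop at 7 or more withdrawals and restate its properties. Those are alpha 0.037, power 0.704, early termination 0.818 and EN 20.09 if withdrawal equals failure, with a range for other assumptions. The choice is the sponsor's.
3. **Reconcile 8.1.11 and 8.2.11 with 10.2** on the 12-participant stop.
4. **State one denominator** that reconciles 6.2, 6.8 and 10.3.
5. **If stage 1 has already been decided,** keep that decision and restate the operating characteristics that applied. Redefining the rule after outcomes are visible would be post hoc. This may well be the live case. The initial version is dated November 2016 and Amendment 8 October 2022, and at section 3.0's planned rate of at least 2 a month, 63 patients take at most 63/2 = 31.5 months. Actual accrual is not given.

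The cost is wording and a short recalculation, with no change in sample size. The downside is that the stated power may be less favourable than 0.804. If a separate withdrawal stop is kept beside a futility look, its effect on power must be included.

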10.3 Data Analyses Plans

Response rates and 95% confidence intervals will be calculated using exact binomial probability distributions for discrete outcomes. Progression-free survival and overall survival will be graphically depicted using Kaplan-Meier curves. Adverse events will be summarized descriptively using frequencies and percentages. Statistics will be given on type, severity, frequency and attribution of adverse events. Sample size considerations are described above.

An intention to treat analysis will be done. In a single group Phase II study, intention to treat means that all patients who are evaluated and registered for the study are followed and analyzed regardless of (a) whether they were subsequently found to be protocol ineligible and (b) the amount of study treatment (nivolumab/ipilimumab) they received. To calculate progression-free and overall survival in patients who received nivolumab/ipilimumab, times will be taken from the time of study registration. This definition parallels the definition of intention to treat in randomized clinical trials.

11.0 STUDY MANAGEMENT REFERENCES

11.1 Institutional Review Board (IRB) Approval and Consent

It is expected that the IRB will have the proper representation and function in accordance with federally mandated regulations. The IRB should approve the consent form and protocol.

In obtaining and documenting informed consent, the investigator should comply with the applicable regulatory requirement(s), and should adhere to Good Clinical Practice (GCP) and to ethical principles that have their origin in the Declaration of Helsinki.

Before recruitment and enrollment onto this study, the patient will be given a full explanation of the study and will be given the opportunity to review the consent form. Each consent form must include all the relevant elements currently required by the FDA Regulations and local or state regulations. Once this essential information has been provided to the patient and the investigator is assured that the patient understands the

NU Study Number: NU 16N03
BMS Study Number: CA 209-802

implications of participating in the study, the patient will be asked to give consent to participate in the study by signing an IRB approved consent form.

Prior to a patient's participation in the trial, the written informed consent form should be signed and personally dated by the patient and by the person who conducted the informed consent discussion.

11.2 Amendments

The Principal Investigator will formally initiate all amendments to the protocol and/or informed consent. All amendments will be subject to the review and approval of the appropriate local, institutional, and governmental regulatory bodies, as well as by BMS. Amendments will be distributed by the lead institution (Northwestern) to all affiliate sites upon approval by the Northwestern University IRB.

11.3 Registration Procedures

Patients may not begin protocol treatment prior to registration. All patient registrations will be registered centrally through the Clinical Research Office at Northwestern University before enrollment to study. Please contact the assigned Quality Assurance Monitor (QAM) or email the QA Department ([contact]) for questions regarding patient registration.

Prior to registration, eligibility criteria must be confirmed by the assigned QAM. The study coordinator will screen all subjects for potential registration via the web-based application NOTIS (Northwestern Oncology Trial Information System), which is available at: <https://notis.nubic.northwestern.edu>. Please note that a username and password is required to use this program, and will be provided during site activation prior to training on the NOTIS system. Training on eCRF completion will be provided at the time of site activation.

BEFORE a patient can be treated on study, please complete and submit the following items to confirm eligibility and receive an identification number:

- Patient's signed and dated informed consent form (upload to NOTIS and keep original hard copy in a secure location/study chart)
- Eligibility checklist (signed and dated by the treating physician – upload to NOTIS)
- Eligibility eCRF (complete in NOTIS)
- Copy of the pathology report (upload to NOTIS)

The QAM will review the registration, register the patient, assign a subject identification number, and send a confirmation of registration to study personnel. Registration will then be complete and the patient may begin study treatment.

11.4 Data Submission

Once a subject is confirmed and registered to the study, eCRFs should be submitted according to the detailed data submission guidelines (provided in a separate document). Generally, all data are due at the end of each cycle.

11.5 Instructions for Participating Sites

Before the study can be initiated at any site, the following documentation must be provided to the Clinical Research Office at Northwestern University:

- Signed and completed Letter of Invitation to participate in the study.
- Signed copy of Northwestern University's Data Monitoring Committee policy pertaining to data submission.
- Draft informed consent form should for review/approval prior to submission to the local IRB
- A copy of the official IRB approval letter for the protocol and informed consent.

NU Study Number: NU 16N03
BMS Study Number: CA 209-802

- CVs and medical licensure for the local PI and any sub-investigators who will be involved in the study at the site.
- Form FDA 1572 appropriately filled out and signed with appropriate documentation.

Additional activities may be required prior to site activation (i.e. contract execution, study-specific training). Full requirements will be outlined in a memo upon receipt of the signed Letter of Invitation.

